#### **BHS Screening Promotion**

1. The Bone Health Nurse (BHS RN) will identify eligible patients quarterly as described previously. Patients will be contacted via letter and telephone, and if they agree will be scheduled for DXA.
2. The BHS RN obtains DXA results, calculates Fracture Risk Assessment Tool (FRAX) score, and those meeting treatment thresholds are referred to the Bone Health MD for e-consult.
3. The Bone Health MD reviews additional clinical information in the EHR and generates an e-consult containing recommendations for additional laboratory evaluation (if needed) and treatment; this note is co-signed by the PACT provider. The BHS RN then contacts the patient to provide education and shared decision making, and places orders for PACT provider co-signature.

#### **BHS Adherence Promotion**

1. All patients initiating bisphosphonates will be called by the BHS RN at 1, 6, and 12 months to identify adherence barriers using a validated tool modified for osteoporosis therapy.

Algorithms for overcoming patient and health-care system adherence barriers to osteoporosis medications will be used in these calls (appendix 1). For example, patients reporting gastrointestinal distress will be offered annual intravenous therapy; patients with difficulty ordering refills will be assisted to enroll in *myhealththevet*. The 12-month call will ensure that the medication has been re-ordered. Subsequently, patients not refilling medications will be identified from RDW every 6 months, with telephone follow-up as indicated.

2. Patients with medication nonadherence identified during these calls will be offered an additional educational visit, based on the content of a prior successful osteoporosis adherence promotion program. The educational program will be delivered by the BHS RN during a group visit, Virtual Medical Room visit, or telephone visit at the Veteran's choice.

*Table 2. Model components by step in the Screen and Treat Process. All steps represent usual clinical care for the Veteran.*

Step in Process	Control	PACT Practice Management (removed from study activities)	Bone Health Service (BHS)
Screening Promotion			
Selection for screening	Discretion of provider	List of eligible patients provided to PACT RN biannually	BHS RN queries RDW quarterly
Scheduling screening	Provider orders; MSA or Veteran phone call to radiology	PACT RN orders; MSA or Veteran phone call to radiology	BHS RN orders and coordinates scheduling with Veteran
Quantify risk from DXA results, determine if they meet treatment threshold	Discretion of provider	Provider accesses FRAX link on Osteoporosis order set	BHS RN and BHS MD based on FRAX risk
Shared decision-making with Veteran	Provider by phone or at next primary care visit	Provider by telephone or at next primary care visit, patient education materials available	E-consult to provider, BHS phone call with Veteran, decision- tool sent to patient
Adherence Promotion			
Ordering treatment	Provider	Provider on Osteoporosis Order Set	BHS RN with provider co-signature
Adherence monitoring	Discretion of provider	List of non-adhering patients provided to PACT Pharmacist quarterly	BHS RN telephone follow-up and personalized barrier assessment
Intervening when non-adherence detected	Discretion of provider	PACT Pharmacist phone call or visit	BHS RN uses adherence algorithm, educational visit

## Adverse Events

Potential risks to PACT providers include disclosure of confidential demographic information, disruption or change of usual workflow, and emotional discomfort sharing information in a

nominal group technique session. Potential risks to the Veterans include disclosure of protected health information.

All adverse events will be reported per Durham VAMC requirements. All Serious, Unanticipated and Related adverse events will be reported to IRB within 5 business days of hearing of the event. All other adverse events will be reported at continuing review.

### **Costs and/or Payments to Subjects**

There are no costs to subjects. Beginning in year 4, a subset of patients will be given a repeat DEXA scan. For their time, patients will be compensated \$50. A total of 900 patients will be compensated using standard VA compensation policies.

### **Data and Safety Monitoring**

Although this is a low-risk study that is promoting guideline-recommended care, a data safety monitoring board will be recruited to include at least 1 ambulatory care clinician and 2 additional members from the Durham HSR&D COIN. The DSMB will meet biannually to review subject recruitment, data collection and management procedures, and safety outcomes. Screening rates at the PACT level will be measured at baseline and 2 years after implementation. Adverse drug effects related to osteoporosis medications will be evaluated by the DSMB every 6 months. Inadvertent data disclosures will be reported to the DSMB, IRB and VA ORD as soon as discovered, and immediate steps to minimize sharing will be taken.

### **Withdrawal of Participants**

PACT Providers may choose to withdraw their team at any time with no consequence to them or their patients. No further data collection will be completed on their PACT team, and there will be no end-of-study visit. Study staff will request an in-person or phone meeting with the provider to assess reasons for withdrawal.

If a Veteran wishes to withdraw, he/she can do so by contacting our study team in writing or verbally. There are no anticipated circumstances under which subjects will be withdrawn without their consent.

### **Data Collection, Flow and Management**

Provider-level data is limited to demographic information and is collected on a paper form at the time of informed consent and entered into the study database. Paper forms are stored in the Durham GRECC as above.

Patient-level data from both Durham and Richmond VAMCs is downloaded directly from the Regional Data Warehouse on an excel spreadsheet, and uploaded into the study database behind the VA firewall. Additional data fields are abstracted by study staff from CPRS directly into the study database. The study database is maintained in a secure HSR&D drive folder <\\vhadurhsmcifs01.v06.med.va.gov\HSDR\PMOPS>. Data will not be transferred to outside entities.

## Data Analysis and Statistical Considerations

Data for Aims 1 and 2 will be analyzed by the study statisticians ([name], [name]) on the HSR&D server using the most currently available version of SAS. Nominal Group Technique data will be analyzed using qualitative methods by the PI ([name]) and other relevant study staff on the HSR&D server. Aggregated, population-level data for aim 3 economic analyses will be provided to the study economist ([name]) at the Salt Lake City VAMC using TreeAGE software.

propensity score matching) to make the groups conditionally equal. The parameter of interest will be the Group mean (and standard error) over time, and measured by the ‘average’ PACT value at each time point. Finally, we note that the estimation models above can be adapted to

outcomes distributed other than normal, including Poisson (for number of events/time) and binary (for binary events). This is a 2 group by 3

[figure not shown]

Figure 6. Markov model for Aim 3 analyses of economic impact of 3 screening models.

yearly time point design. To control the overall Type-I error level, we will use the baseline time point as a baseline covariate, and assess group differences at the following time points controlling for baseline. Level of statistical significance will be set at 0.05 (two-tailed) for all tests. In this work, we proposed a GroupxTime interaction, using the time effects as classes/factors. Depending on the significance of this omnibus test, we can assess tests of individual differences (say, group differences at a specific point) by gate-keeping strategy. In the case where the omnibus group by time interaction is significant, then, these will be done without a Type-I error penalty. Initially, we will assess a Time by Group interaction (on 1 degree of freedom). If that effect is declared statistically significant, we will perform follow-up tests to determine where the group differences exist at each follow-up time point, using the gate-keeping strategy listed above. If the Group by Time interaction is not significant, then the main effects of Group and Time will be tested.

Aim 3. Prior Markov models of osteoporosis screening have been adapted for this study (Figure 6). A Markov cost-utility model with 6 health states will be constructed comparing 3 different strategies of DXA screening, followed by 5 years of treatment with alendronate (the most commonly prescribed medication) for those with a femoral neck T-score of  $<-2.5$  or FRAX 10 year fracture risk above current treatment thresholds (3% hip, 20% major osteoporotic fracture). For the base-case analyses, the model will be run for five different starting ages (65, 70, 75, 80, and 85) using Monte Carlo simulations with 40,000 trials each. Running the models for 5-year increments allows us to adjust the transition probabilities for observed differences over time (e.g., higher fracture rates or different adherence rates with older age). The health states in the model are no fracture, post distal forearm fracture, post clinical vertebral fracture, post hip fracture, post other fractures (humerus, scapula, ribs, pelvis, distal femur, pelvis, patella, tibia, or proximal fibula), and death. Following the recommendations of the 2nd Panel on Cost-

Table 5. Data Sources for Aim 3 (see also Health Systems Policy Outcomes Section)

Data Category	Source(s)
Proportion screened and treated	Aggregated aim 1 results
Medication adherence, persistence	Aggregated aim 1 results
Bone Mineral Density	Random sample of 712 men (356 UC, 178 each of the other 2 models) eligible for screening in panel at least 1 year, measured 2 years after start date
Treatment efficacy	Published efficacy for bisphosphonates by medication adherence and persistence rates
Fracture rates	National VA data (preliminary results)
Fracture costs	National VA and CMS data including Fee Basis and CHOICE costs (preliminary results)
Screening and Treatment costs	Aim 2 results, current VA/CMS DXA cost, rare serious harm estimates from population data
Fracture disutility	Systematic review of disutility by fracture type

Effectiveness in Health and Medicine, we will analyze our model from both the VA and societal perspectives and present our results as an impact inventory.

The direct and indirect costs of that fracture will be assigned as a transition cost. The disutility associated with these fractures will be modeled as a QALY decrement associated with that fracture state based on a published systematic review of fracture disutility rates and is assigned for 6 months upon which they return to baseline state, except for hip and vertebral fractures for which permanent disutility is the norm. If an individual suffers an additional fracture, the costs of that fracture are assigned, but the person remains in the post vertebral or post hip fracture state because the long-term disutility associated with prior vertebral and hip fractures is greater. Long-term care costs beyond the first year after hip fracture are assigned as a cost per year. Individuals in the model will be eligible (at risk) of transition to a different state once every 3 months, and a maximum of 2 fracture types is assumed. We will parameterize our model using inputs derived from Aims 1 and 2 of the current grant and from the published literature. A discount rate of 3% will be assumed for costs and health benefits.

Treeage software will be used for analyses. One-way sensitivity analyses will be performed varying discount rates, fracture rates, fracture costs, fracture disutility, costs of DXA, the onset

and offset of fracture reduction benefit following initiation and cessation of drug therapy, medication adherence, the relative risks of fractures attributable to osteoporosis or prior clinical fracture, cost of screening and yearly bisphosphonate. Because of uncertainty regarding the nonvertebral fracture reduction efficacy of oral bisphosphonates for men, 2-way sensitivity analyses will be performed assuming reduced fracture efficacy. Probabilistic sensitivity analyses will be performed using 2nd order Monte Carlo simulations in which each parameter value will be drawn from a distribution with characteristics specific to that parameter. For example, log-normal distributions of fracture direct costs and normal distributions of fracture rates and long-term care costs following hip fracture. The distributions of the relative risks of incident fractures associated with osteoporosis, prior fracture, and oral bisphosphonate therapy are assumed to be log-normal. Uniform distributions will be used to model variability in fracture disutility and indirect fracture costs. Results from the PSA will be presented as scatterplots on the cost-effectiveness plane and as cost effectiveness acceptability curves.

**Nominal Group Analysis.** During structured group discussion and voting, each nominal group generates a list of statements in response to each question, and rank orders them on order of importance. To analyze the resulting data, we will first generate a spreadsheet for each question listing the group-generated statements, scores, and average score (total score/number of group members) by group. The statements from each group will be entered into Atlas.ti, and content analysis used to generate themes recurring across groups. Themes will be generated independently by the PI who has extensive experience in qualitative analysis and the Project Director who will engage in additional qualitative training for this project (see budget justification). A code book will be developed in an iterative manner, and confirmatory content analysis completed independently by co-investigator [name] to enhance reliability. All statements will then be coded by at least 2 independent investigators. Once the data is coded, final analysis will proceed in 2 steps. **1) Generation of top 7 themes for each question.** Although each group responds to the same questions, because they work

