### **Specific aims:**

1. Compare the impact of BHS primary osteoporosis screening models on **patient level outcomes** strongly associated with fractures as measured by the EHR at 2 years; 1) eligible proportion screened; 2) medication adherence (initiation; implementation, and discontinuation); 3) bone mineral density at the femoral neck in a random sample of high risk patients. Fracture rates (fractures/patient years) are exploratory.

H1a: PACT teams randomized to BHS will have better patient level outcomes compared to usual care at pre-specified clinically important levels, adjusting for baseline levels.

2. Determine the impact of BHS primary osteoporosis screening models on **provider and facility level outcomes** including change in DXA volume, change in metabolic bone disease clinic volume (assessed by EHR), and PACT provider time and satisfaction (assessed by Nominal Group Technique).

H2a: DXA and metabolic bone disease clinic volumes will increase during the intervention, with a higher proportion of referrals coming from PACTs randomized to BHS.

H2b: Provider satisfaction with osteoporosis screening systems will be higher for PACTs randomized to BHS management compared to usual care.

3. Determine the impact of BHS primary osteoporosis screening programs on **health system and policy level outcomes** using Markov models of screening program cost per quality adjusted life year. Model inputs are based on VA national fracture data from our prior work, results from aims 1 and 2, and published quality of life estimates.

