## Design

Pragmatic group randomized trial of PACT teams (n=39 teams recruited, estimated 24 at DVAHS and 15 at Richmond VAMC) will be randomized into 2 groups: a control group (no additional support, and a centralized Bone Health Service (BHS) model. Outcomes for all patients eligible for osteoporosis screening within the randomized PACTs will be assessed by investigators masked to group assignment via EHR at baseline and 2 years. Outcomes for PACT providers will be assessed using qualitative methods (nominal group technique).

**Outcome measures** are listed in the table 1 below.

Table 1. Outcome measures by Aim. RDW=Regional Data Warehouse; MPR=Medication Possession Ratio; FRAX=Fracture Risk Assessment Tool.

Outcome	Definition/Measure	Data Source/Timing	Important Difference
Patient (Panel) Level (Aim 1)			
Screening Rates	Proportion of eligible men screened in last 12 months	RDW at baseline, year 1 and year 2	25% increase from 6% Control
Medication Initiation	Proportion of screened men meeting treatment threshold (T score $\leq -2.5$ or FRAX score high-risk) who receive at least 1 prescription	RDW, intervention period year 1 and year 2, non-VA medication lists by chart abstraction.	30% increase from 55% Control
Medication Implementation	Days of medication dispensed divided by follow-up days	Pharmacy dispensing records, for patients started within prior year at baseline, year 1 and 2. Non-VA medication lists by chart abstraction.	20% increase in MPR $>80\%^{14}$ from 30% Control
Medication Discontinuation	Time between first prescription dispensing date and the date of first medication possession gap of $\geq 3$ months	Pharmacy dispensing records, for patients started within prior year at baseline, year 1 and 2. Non-VA medication lists by chart abstraction.	20% difference
Bone Mineral Density	BMD g/cm  at femoral neck and lumbar spine in random sample of men eligible for screening	Random sample of 712 men (356 UC, 178 each of the other 2 models) eligible for screening in panel at least 1 year, measured 2 years after start date	Post-intervention between group difference of 3% femoral neck, 5% lumbar spine 
Harms	Proportion of men started on oral medication for new GI distress in 3 months  Subtrochanteric fractures or Osteonecrosis of the jaw	RDW ICD10 codes, new prescription for proton pump inhibitor or H2 blocker.  RDW ICD10 codes	15% increase from 30% Control  >expected 1/50,000 patient years treatment

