Screening Tool calculation. We do not expect attrition as new patients are added as others leave with relatively constant panel size. Finally, we determine power for the single degree of freedom contrast of import – Usual Care vs. BHS groups across the follow-up time points. For each of the individual outcomes, assumptions and power requirements are listed in the Table. A sample size of 39 PACTs (19 BHS vs. 20 Usual Care) with an average 100 patients / PACT provides over 85% power for all our primary patient-level outcomes, except fracture rates - an exploratory analysis.

Table 6. Power calculation assumptions for Aim 1

Outcome	Assumptions, Minimal Clinically Significant Difference	Power for 39 PACTs and 3900 patients
Screening Rates (PACT level)	6% Usual Care, 40% new models	>0.99
Osteoporosis Treatment	Assume 25% of screened meet treatment thresholds. 30% increase from 55% Usual Care	>0.99
Medication Adherence	Usual Care MPR 0.60 (SD 0.35). 20% increase	0.85
Bone Mineral Density (BMD) Femoral Neck in random sample of high-risk patients	0.939 g/cm  in BHS group vs. 0.967 Usual Care with SD pooled =0.133	0.90 for random sample of 952 patients (25/team); 0.80 for 712 (19/team)

**Missing data Strategies.** As is standard in administrative databases, the absence of a diagnosis code (e.g., fracture) will be assumed to indicate that the event did not occur, and coded by default as 'not present'. For continuous measures where zero is illogical, we will impute a value, simulate and use bootstrapping to derive estimates of effect with appropriate standard errors. To implement the multiple imputation techniques for primary analyses, we will use preliminary analyses of such associations, including graphical displays, to investigate the plausibility of the assumptions underlying the imputation model employed. Further, we will use 25 or more imputed data sets, with FU bootstrapped estimates in order to reduce the impact of the random sampling.

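### Aim 1 tests several primary outcomes, each at two-sided 0.05, with no order, alpha split or rule for when H1a is met, so error across outcomes is not controlled

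*Protocol*

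**What the plan says.** **Outcomes.** Aim 1 in the Protocol's Specific aims lists "1) eligible proportion screened; 2) medication adherence (initiation; implementation, and discontinuation); 3) bone mineral density at the femoral neck", which makes five. Table 1 (Design) adds a second BMD site: "Post-intervention between group difference of 3% femoral neck, 5% lumbar spine". The Power paragraph says the sample size "provides over 85% power for all our primary patient-level outcomes, except fracture rates - an exploratory analysis". So the word primary covers several outcomes, and Table 6 gives power for four of them: screening, treatment, adherence and femoral neck BMD.

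**Hypothesis.** H1a is a single statement: "PACT teams randomized to BHS will have better patient level outcomes compared to usual care at pre-specified clinically important levels". It does not say whether one outcome, some or all must succeed.

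**Testing.** Under Aims 1 and 2: "Level of statistical significance will be set at 0.05 (two-tailed) for all tests". The sentence on overall error is "To control the overall Type-I error level, we will use the baseline time point as a baseline covariate", and it continues by assessing group differences at the later time points. If the Group by Time test is significant, "we can assess tests of individual differences (say, group differences at a specific point) by gate-keeping strategy", with no penalty for those follow-up tests. If it is not, the main effects of Group and Time are tested.

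The SAP's Revised Specific Aims and Revised Analysis Plan repeat all of this for the two-arm design. I found no order, alpha split or adjustment across outcomes in either document.

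**The concern.** The plan speaks of controlling overall Type I error, but both devices it offers work inside one outcome. Using baseline as a covariate takes baseline out of the set of tested time points and may improve precision. The gate-keeping runs from the Group by Time test to single time points. Neither takes account of the same 0.05 being spent again on each further outcome.

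The decision rule for H1a is therefore left open. With four to six outcomes each at 0.05, whichever one reaches significance could be presented as support for H1a, and nothing written in advance would rule that out.

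**Working it through.** **1. How much alpha the plan spends on one outcome.** Table 6 gives femoral neck BMD a difference of 0.967 − 0.939 = 0.028 g/cm² (size only) and an SD of 0.133. Power is Φ(0.028 / (0.133·√(2/n)) − 1.96), with n per arm.
- N = 952, n = 476: 0.028/0.00862 = 3.25; Φ(1.29) = 0.901. Stated: 0.90.
- N = 712, n = 356: 0.028/0.00997 = 2.81; Φ(0.85) = 0.802. Stated: 0.80.

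Both reproduce, so the full two-sided 0.05 goes to this one outcome. (The match uses no design effect for clustering, which is a separate matter.)

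**2. Error across k outcomes.** There is one test per outcome at 0.05, no true difference on any outcome, and a claim if any one is significant.
- Either direction, independent: 1 − 0.95^k.
- Favouring BHS only, independent: 1 − 0.975^k.
- Correlated outcomes: equicorrelated normal statistics, by numerical integration (either direction) or simulation with 400,000 draws (BHS only). The documents give no correlations, so the range 0 to 0.7 is an assumption.

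| k | Either direction: independent | 0.3 | 0.5 | 0.7 | Favouring BHS: independent | 0.7 |
|---|---|---|---|---|---|---|
| 4 (Table 6) | 18.5% | 17.4% | 15.6% | 13.0% | 9.6% | 6.5% |
| 5 (aims) | 22.6% | 20.9% | 18.3% | 14.8% | 11.9% | 7.3% |
| 6 (with lumbar spine) | 26.5% | 24.1% | 20.7% | 16.4% | 14.1% | 8.2% |

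The reference for a single test is 5% in either direction and 2.5% favouring BHS. Even at correlation 0.9, the either-direction figure is 9.4% (k = 4) to 10.8% (k = 6).

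**3. If screening truly works.** Three other Table 6 outcomes remain. If independent, the chance of a false difference among them is 1 − 0.95³ = 14.3% in either direction, and 1 − 0.975³ = 7.3% favouring BHS.

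**4. What the table leaves out.** Within each outcome the plan has two routes: the interaction, then the main effect if the interaction is not significant. I simulated both, requiring a significant group difference and assuming a between-year correlation of 0.3 to 0.7 and a between-outcome correlation of 0 or 0.7. One outcome alone gives about 6–7% in either direction. Four to six outcomes give about 16–36% in either direction, and 8–20% favouring BHS.

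**5. What control would cost in BMD power, by the plan's own formula.** Bonferroni over four outcomes (0.0125 each) gives 0.77 at N = 952 and 0.62 at N = 712. In a fixed sequence with screening first (stated power above 0.99), BMD keeps 0.05, and its power falls by at most 0.01: at least 0.89 and 0.79.

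**The case against.** **The baseline sentence is about time points.** It directly follows the description of the design as two groups by three yearly time points, and the interaction is put on 1 degree of freedom, which fits two follow-up times. This stands. A reader might infer that the plan claims baseline adjustment protects against multiple outcomes, and that the claim is false. The text does not clearly say that. The word overall is loose, and once the sentence is read in context nothing is left that acts across outcomes.

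**H1a is directional.** A reader might infer that the chance of a false H1a claim is 13–26%. That range counts false results in both directions, and a result against BHS cannot support H1a. The figure for H1a is the BHS-only one.

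**Six is not a settled count of primary outcomes.** Table 6 powers four, and lumbar spine BMD is absent from the aims. Four is the firmer basis; six is the upper end.

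**H1a may ask for more than p < 0.05.** It refers to clinically important levels, and Table 1 lists a difference for each outcome. If an observed 3% BMD difference (0.029) were required, then by the unclustered formula z would be 3.36 at N = 952 and 2.91 at N = 712, with one-sided null probabilities of about 0.0004 and 0.002. If every outcome had to succeed, no adjustment would be needed. Either rule would answer the concern, but neither is stated, and the wording can equally describe design targets.

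**Screening will almost certainly differ** (6% against 40% assumed). That is likely, but the remaining outcomes are still each tested at an unadjusted 0.05 (step 3).

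**Conclusion.** The point holds: the plan has several primary outcomes and no rule across them, and following it as written does not hold error across outcomes at the single-test level. For the four powered outcomes, a false result favouring BHS has probability 6.5–9.6% rather than 2.5%, and a false difference in either direction 13–19% rather than 5%. With all six outcomes of Table 1 the upper ends are 14% and 26%.

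These figures rest on four assumptions: any one significant outcome may support H1a, there is one test per outcome, correlations lie between 0 and 0.7, and there is no true difference on any outcome counted. The one-test assumption makes the figures low if both routes within an outcome count. The any-one assumption makes them high if the sponsor meant H1a to need every outcome, or a difference of the listed size. The documents do not settle which was meant.

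**What to change.** In the Protocol (Aims 1 and 2) and the SAP's Revised Analysis Plan:

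1. Reword the baseline sentence so that it claims control only over time points within an outcome.
2. Before outcomes are analysed, state one rule across the Aim 1 outcomes and when H1a is met. One example is a fixed sequence: screening first at 0.05; femoral neck BMD second at 0.05 only if screening is significant; initiation, implementation, discontinuation and lumbar spine BMD either later in the sequence or secondary with nominal p-values. Another order, or one named primary outcome, would also do; the choice is the sponsor's.
3. Say which single test of each outcome counts for that rule, since the two routes within an outcome would otherwise carry extra error into the sequence.

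The cost is wording. No extra patients are needed, and BMD power stays close to the stated 0.90 or 0.80. The downside is that outcomes placed later, or made secondary, cannot support H1a on their own.

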
yearly time point design. To control the overall Type-I error level, we will use the baseline time point as a baseline covariate, and assess group differences at the following time points controlling for baseline. Level of statistical significance will be set at 0.05 (two-tailed) for all tests. In this work, we proposed a GroupxTime interaction, using the time effects as classes/factors. Depending on the significance of this omnibus test, we can assess tests of individual differences (say, group differences at a specific point) by gate-keeping strategy. In the case where the omnibus group by time interaction is significant, then, these will be done without a Type-I error penalty. Initially, we will assess a Time by Group interaction (on 1 degree of freedom). If that effect is declared statistically significant, we will perform follow-up tests to determine where the group differences exist at each follow-up time point, using the gate-keeping strategy listed above. If the Group by Time interaction is not significant, then the main effects of Group and Time will be tested.

**Power.** We estimate power using aim 1 (patient level) outcomes. The power-limiting endpoint of interest is BMD. We can feasibly invite 100 patients for primary screening in each BHS team given DXA capacity and staff limitations. To achieve 90% power for our minimally clinically significant change in BMD, we will randomly select 25 (25%) from these patients and the top 100 highest risk patients in the Usual Care teams. Recruitment of 712 patients (19/team) will still provide 80% power to detect this difference. Power for the feasibility and acceptability endpoints exceeds 85% with this sample size.

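### The Group-by-Time sequence gives two routes to a BHS claim, each at the full 0.05, so the stated control of overall Type-I error is not delivered for outcomes measured at years 1 and 2

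*Protocol*

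**What the plan says.** The testing sequence is in the protocol under Aims 1 and 2 and is repeated in the SAP's Revised Analysis Plan, which replaces the three-arm scheme earlier in that document.

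- Level: "Level of statistical significance will be set at 0.05 (two-tailed) for all tests".
- Stated error control: "To control the overall Type-I error level, we will use the baseline time point as a baseline covariate". Years 1 and 2 are then the two tested times.
- First step: a Group-by-Time interaction on one degree of freedom.
- If the interaction is significant, the groups are compared "to determine where the group differences exist at each follow-up time point". On those comparisons the plan says: "In the case where the omnibus group by time interaction is significant, then, these will be done without a Type-I error penalty".
- Otherwise: "If the Group by Time interaction is not significant, then the main effects of Group and Time will be tested".

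Two other statements bear on the remedy. The same section says: "The parameter of interest will be the Group mean (and standard error) over time". The Power paragraphs of both documents name the powered contrast as "Usual Care vs. BHS groups across the follow-up time points". Neither statement makes that contrast the one unconditional test.

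In protocol Table 1, screening and medication implementation are measured at baseline, year 1 and year 2. Medication initiation is listed for years 1 and 2 only. Bone mineral density has a single measurement, two years after the start.

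**The concern.** With two follow-up times, the interaction asks only whether the BHS effect differs between year 1 and year 2. The gatekeeping therefore protects only the year-specific tests. When the gate fails, a second path to the same conclusion opens at the full 0.05. Baseline adjustment does not divide alpha between the two paths, and Table 1 lists no baseline measure for initiation at all.

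Two further points are open, and both affect the error rate:

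- **Which year carries the claim.** The testing text looks at each follow-up time, while the Specific aims and the Design paragraph place the outcomes at 2 years.
- **How the main effect weights the two years.** It could weight them equally or by precision.

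What is at stake is whether a nominal p<0.05 means what the plan says it means. Screening and initiation, with stated power above 0.99, are unlikely to change. Medication adherence, with stated power 0.85, is the most exposed.

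**Working it through.** **Inputs.** From the documents: two-sided 0.05 for every test, two follow-up times, a one-degree-of-freedom interaction as the first test, and 19 BHS against 20 Usual Care PACTs. Not in the documents: the correlation rho between the year-1 and year-2 group differences, and the ratio r of the year-2 to the year-1 standard error (SE). I take rho from 0 to 0.9 and r from 0.5 to 2.

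**The plan's own figure.** The plan gives 0.05 per test and no error rate for the whole sequence. Taken singly, the interaction test and the main-effect test each have size 0.05 at |Z|>1.96.

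**Equal SEs (r = 1).** Let Z1 and Z2 be the standardised group differences at the two years.

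- Interaction: I = (Z2 − Z1)/√(2(1 − rho))
- Main effect: M = (Z1 + Z2)/√(2(1 + rho))

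With no BHS effect in either year, I and M are independent standard normals. The main-effect route contributes

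P(|I| ≤ 1.96) × P(|M| > 1.96) = 0.95 × 0.05 = 4.75%.

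The interaction route adds P(|I| > 1.96 and a qualifying year test is significant), found by numerical integration:

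| rho | Added, either year | Total | Added, year 2 only | Total |
|---|---|---|---|---|
| 0 | 3.25% | 8.0% | 1.69% | 6.4% |
| 0.3 | 2.42% | 7.2% | 1.22% | 6.0% |
| 0.5 | 1.85% | 6.6% | 0.93% | 5.7% |
| 0.7 | 1.29% | 6.0% | 0.65% | 5.4% |
| 0.9 | 0.71% | 5.5% | 0.38% | 5.1% |

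Simulation with 4 million draws agrees. So does a simulation of 19 against 20 PACT means with t tests on 37 degrees of freedom: at rho 0, 0.5 and 0.9 it gives 8.0%, 6.6% and 5.4% (either year) and 6.4%, 5.7% and 5.1% (year 2).

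**Unequal SEs.** Ranges over rho 0 to 0.9:

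| Reading | Main effect | r | False-positive rate |
|---|---|---|---|
| Either year | equal weights | 0.5 to 2, except 1 | 5.6% to 7.8% |
| Either year | precision weights | 0.5 to 2, except 1 | 6.6% to 8.3% |
| Year 2 only | equal weights | 0.5 | 3.7% to 4.5% |
| Year 2 only | equal weights | 0.71 | 4.3% to 5.6% |
| Year 2 only | equal weights | 1.41 and 2 | 5.6% to 6.8% |
| Year 2 only | precision weights | 0.5 and 0.71 | 5.0% to 6.3% |
| Year 2 only | precision weights | 1.41 and 2 | 6.4% to 8.0% |

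Ignoring clustering, r = 0.5 needs about (1/0.5)² = 4 times as many men contributing in year 2 as in year 1, and r = 0.71 about (1/0.71)² ≈ 2 times as many.

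**Power of the alternatives (r = 1).** The year-2 effect is fixed at (1.96 + 1.036) × √((1 + rho)/2) SE units. At that size the across-time contrast has power 0.85 when the effect is the same in both years. Ranges are over rho 0 to 0.9; the current rule is shown with either year counting.

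| Year-1 effect relative to year 2 | Across-time contrast | Current rule | Year-2 contrast |
|---|---|---|---|
| Same | 0.85 | 0.85–0.86 | 0.56–0.83 |
| Half | 0.61 | 0.65–0.82 | 0.56–0.83 |
| None | 0.32 | 0.51–0.86 | 0.56–0.83 |

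If only year 2 counts, the current rule has 0.50–0.83 in the last row.

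**The case against.** The strongest reply is that the size of the excess rests on assumptions.

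- **Year 2 may be the claim, and may be the more precise year.** The SAP's project modification request reports DXA testing resuming at 20–30% capacity, so early data may be thinner. With a year-2 claim and an equal-weight main effect, the rate is then mostly at or below 5%. This stands, and it limits how firmly any one figure can be stated.
- **The 8.0% figure is an extreme.** At correlation 0, about 96% of the positives from the interaction route have opposite signs in the two years (80% at 0.3, 50% at 0.5). Zero correlation also suits screening poorly. If PACT effects are stable and there are 100 men per PACT, an assumed intraclass correlation (ICC) of 0.01 makes 100 × 0.01/(1 + 99 × 0.01) ≈ 50% of the PACT-mean variance shared between years, and 0.05 makes it about 84%. Either-year rates are then about 6.6% and 5.6–5.7%. The argument is weaker for medication outcomes, which have fewer men per PACT.
- **The rates are two-sided.** False claims favouring BHS are about half: 4.1% to 2.7% (either year) and 3.2% to 2.6% (year 2), against a nominal 2.5%.
- **A few precision-weighted cells are artificial.** When the correlation exceeds the ratio of the smaller to the larger SE, one year gets a negative weight. Without those cells, the year-2-only upper limits of 6.3% and 8.0% become about 5.9% and 7.7%.
- **The plan already names a suitable contrast.** It does, in the Power paragraphs, but it does not make that contrast unconditional.
- **The across-time contrast gives up power if the effect is delayed.** This is true, and it is a choice for the sponsor to make openly.

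None of this restores error control to the sequence as written. On the either-year reading, every case computed exceeds 5%.

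**Conclusion.** The concern holds. Both documents contain two routes to the same claim, each at 0.05 with no division, and the device offered for overall Type-I control does not address this.

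That structural point needs no assumption; the size of the excess does. It is modest, largest when the two years are uncorrelated, and nearly gone at a correlation of 0.9. It can reverse on the year-2 reading when year 2 is the more precise year. The actual error level therefore depends on which year carries the claim and how the main effect is weighted, neither of which the plan states.

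The rates are per outcome and do not cover multiplicity across the Aim 1 outcomes. The sponsor should correct this before analysis.

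**What to change.** For each repeated Aim 1 outcome, name in advance one unconditional two-sided 0.05 test of BHS against Usual Care. There are two sound choices:

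1. **The across-time contrast already used for power**, with its weighting of the years stated. Test year 1 and year 2, each at 0.05, only if this contrast is significant. With two times this is a closed test and holds 5%.
2. **A single year-2 contrast**, if the sponsor regards year 2 as the claim, as the Specific aims suggest. This also holds 5%.

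In either case, report Group-by-Time as descriptive, and state that bone mineral density uses one group contrast at its one time point.

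The choice should be explicit because each option has a cost. The across-time contrast falls to power 0.32 if there is no year-1 effect. The year-2 contrast has 0.56–0.83 where the across-time contrast has 0.85 under a constant effect. Reduced DXA capacity and the staged re-invitations in the SAP's revised timeline make a delayed effect plausible.

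The change is a few sentences in each document, with no new data and no change in sample size.
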